- [17] Tumor imaging evaluation: CT or MRI of lesions in the head, chest, abdomen, pelvis, and other sites. Sites with bone metastasis as shown by bone scans, PET-CT, or clinical indications must also be reexamined by CT or MRI at baseline but no longer undergo bone scan or PET-CT for efficacy follow-up. CT or MRI follow-ups of lesions in the head, chest, abdomen, pelvis, and other sites will be performed at each response evaluation. The CT/MRI examination methods and techniques for a subject shall remain the same throughout the study period.
 - ✓ At screening, tumor evaluations (at this study center only) up to 4 weeks before the first dose and before signing the informed consent may be used as long as they meet the requirements.

- ✓ Study treatment period: The imaging examination cycles will start from C1D1. In the first 16 treatment cycles, imaging examinations will be performed once every 2 cycles (the first assessment will be on C3D1), and once every 4 cycles thereafter. Imaging examinations will no longer be performed in case of radiographic progression; subjects who discontinue the study treatment for reasons other than radiographic progression will still be followed up according to the established cycle. If the previous imaging examination does not show progression and no imaging examination is performed within 4 weeks before the 21-day visit after the last dose, an imaging examination must be performed at the 21-day visit after the last dose. The time window for tumor evaluation is \pm 7 days. Additional tumor evaluations may be performed if PD is suspected (for example, worsening of symptoms).
- [18] Study treatment: (doxorubicin + ifosfamide/ifosfamide monotherapy): doxorubicin 60 mg/m², on D1, ifosfamide 2 g/m²/d, on D1-D4, q3w, and 6 cycles are recommended; if the investigator considers that the subject benefits from the chemotherapy, additional chemotherapy cycles may be administered; the content of visits in subsequent treatment cycles will be the same as those in cycles 2-6. If intolerance is noted, the investigator may delay the administration of this cycle or the chemotherapy drug, and adjust the administration time of the next cycle to 21 days after the administration of the previous cycle. If the maximum cumulative dose of doxorubicin is reached, the treatment will be switched to ifosfamide monotherapy 2 g/m²/d on D1-D5 q3w.
- [19] Adverse events: Recorded from the date of signing the informed consent form to the end of the safety follow-up period or the start of a new anti-tumor treatment. See [Table 11. Principles of AE/SAE collection and follow-up](#) for details.
- [20] Concomitant medication/treatment: Recorded from 28 days before the first dose of study treatment to the end of the safety follow-up period; If a new anti-tumor treatment is started, only concomitant medications for treatment-related adverse events will be recorded thereafter. After the safety follow-up period, only concomitant medications/treatments for adverse events are required to be recorded. Subjects crossed over for SHR-1210 + apatinib treatment will be followed up according to the procedures after crossover.
- [21] Quality of life scoring: Performed within 7 days before the first dose, on day 1 of every 2 cycles in cycles 3-6, on day 1 of every 2 cycles in cycles 7-16, on day 1 of every 4 cycles from cycle 17 onwards, and at 21 days after the last dose.
- [22] Safety visit: Subjects shall go to the study center for safety visit at 21 days after the last dose in accordance with protocol requirements.
- [23] Survival follow-up: At the end of the safety follow-up period, the subjects will enter the survival follow-up period until death, lost to follow-up, withdrawal of informed consent or termination of the clinical study by the sponsor. During this period, follow-up will be conducted via phone calls or other effective methods once every 2 months to collect information on subject survival and subsequent treatments (if the subject starts a new anti-tumor treatment, the therapeutic regimen and the start and end time should be recorded).

3 SCHEDULE OF ACTIVITIES — CROSSOVER TREATMENT (SHR-1210 + APATINIB AFTER PROGRESSION FOLLOWING DOXORUBICIN + IFOSFAMIDE OR IFOSFAMIDE MONOTHERAPY)

STUDY PROCEDURES	Screening Period	Cycle 1	Cycle 2	Cycle 3 and Beyond	Safety Follow-Up ^[22]		Survival Follow-Up ^[23]
	D-7 to D-1	D1	D1	D1 (once per cycle)	30 days after the last dose	60 and 90 days after the last dose	Once every 2 months
Time Window				±3	±5	±5	±5
Signing of Informed Consent and Verification of Eligibility ^[1]	×						
ECOG PS ^[2]	×		×	×	×		
Vital Sign ^[3]	×		×	×	×		
Physical Examination ^[4]	×		×	×	×		
Virology ^[5]	×						
Hematology ^[6]	×		×	×	×		
Urinalysis ^[7]	×			×(once every 2 cycles)	×		
Fecal Occult Blood ^[8]	×		×	×	×		
Blood Biochemistry ^[9]	×		×	×	×		
Coagulation Function ^[10]	×			×(once every 2 cycles)	×		
Thyroid Function ^[11]	×			×(once every 2 cycles)	×		
12-Lead ECG ^[12]	×		×	×	×		
Echocardiography ^[13]	×						
Pregnancy Test ^[14]	×			×(once every 2 cycles)			
Tumor Imaging Examination ^[15]	×(within 28 days)			×(once every 2 cycles or once every 4 cycles)	×		
Dispensation/Retrieval of Drugs and Study Treatment ^[16]		×	×(D-3 to D+7)	×(D-3 to D+7)			

STUDY PROCEDURES	Screening Period	Cycle 1	Cycle 2	Cycle 3 and Beyond	Safety Follow-Up ^[22]		Survival Follow-Up ^[23]
	D-7 to D-1	D1	D1	D1 (once per cycle)	30 days after the last dose	60 and 90 days after the last dose	Once every 2 months
Adverse Events ^[17]	×	×	×	×	×	×	
Concomitant Medications/ Treatments ^[18]	×	×	×	×	×	×	
Pharmacokinetics/Immuno- genicity Blood Sampling ^[19]		×	×	×	×		
Quality of Life Score ^[20]	×			×(once every 2 cycles or once every 4 cycles)	×		
Diary Card Dispensing, Retrieval, and Filling ^[21]		×	×	×			
Subsequent Anti-Tumor Treatment and Survival Status					×	×	×

Note: In addition to the examinations and time points listed in the table, the investigator may add visits and other examinations if needed.

- [1] Subjects in the control group who develop radiographically confirmed progressive disease may be crossed over to receive SHR-1210 + apatinib. There should be at least a 3-week interval between the first dose of SHR-1210 + apatinib and the last dose of the previous standard chemotherapy. The first dose and subsequent visits will be carried out according to the schedule of activities of crossover treatment. Subjects should sign an informed consent form for the crossover treatment. Examination results within 7 days before the first dose of the subject may be used to evaluate whether the inclusion and exclusion criteria of crossover treatment are met (see 8.3.4). If the criteria are met, the subject will receive crossover treatment, i.e., SHR-1210 + apatinib. If the inclusion and exclusion criteria are not met, the subject may receive supportive treatment for adjustment. But during this period, anti-tumor treatment must not be performed. If, at the reexamination 2 months after progressive disease, the inclusion and exclusion criteria for crossover treatment are still not met, crossover to receive SHR-1210 + apatinib will not be permitted.
- [2] ECOG PS scoring: Performed within 7 days before the first dose (*), on day 1 of each cycle from cycle 2 onwards, and at 30 days after the last dose.
- [3] Vital signs: pulse, respiratory rate, temperature, and blood pressure. Performed within 7 days before the first dose (*), on day 1 of each cycle from cycle 2 onwards, and at 30 days after the last dose.

- [4] Physical examination: Performed within 7 days before the first dose (*), on day 1 of each cycle from cycle 2 onwards, and at 30 days after the last dose; comprehensive examinations (height, weight, general condition, head and face, neck, chest, abdomen, perineum, extremities, etc.) will be performed; height will be measured only once within 7 days before the first dose and weight will be measured at each visit point (except C1D1); a targeted physical examination will be performed when clinically indicated.
- [5] Virology: HBsAg (quantitative HBV DNA test if positive); HCV-Ab (quantitative HCV-RNA test if positive) and HIV-Ab.
- [6] Hematology: red blood cell count (RBC), hemoglobin (Hb), blood platelet count (PLT), white blood cell count (WBC), absolute neutrophil count (ANC), and lymphocyte count (LYM); tested within 7 days before the first dose (*), on day 1 of each cycle from cycle 2 onwards, and at 30 days after the last dose.
- [7] Urinalysis: WBC, RBC, and urine protein. If urine protein is $\geq 2+$, then a quantitative 24-h urine protein test should be added; performed within 7 days before the first dose (*), on day 1 of every 2 cycles from cycle 3 onwards, and at 30 days after the last dose.
- [8] Fecal occult blood: performed within 7 days before the first dose (*), on day 1 of each cycle from cycle 2 onwards, and at 30 days after the last dose.
- [9] Blood biochemistry: Alanine transaminase (ALT), aspartate aminotransferase (AST), gamma-glutamyl transferase (γ -GT), total bilirubin (TBIL), direct bilirubin (DBIL), alkaline phosphatase (AKP), blood urea nitrogen (BUN) or urea, total protein (TP), albumin (ALB), creatinine (Cr), blood glucose (GLU), serum potassium (K⁺), serum sodium (Na⁺), serum calcium (Ca²⁺), serum magnesium (Mg²⁺), and blood chloride (Cl⁻); tested within 7 days before the first dose, on day 1 of each cycle from cycle 2 onwards, and at 30 days after the last dose.
- [10] Coagulation function: Activated partial thromboplastin time (APTT), prothrombin time (PT), thrombin time (TT), fibrinogen (FIB), and international normalized ratio (INR); tested within 7 days before the first dose (*), on day 1 of every 2 cycles from cycle 3 onwards, and at 30 days after the last dose.
- [11] Thyroid function: serum thyroid stimulating hormone (TSH), free triiodothyronine (FT3), and free thyroxine (FT4); if FT3 and FT4 are not available, T3 and T4 are allowed for substitution; tested within 7 days before the first dose (*), on day 1 of every 2 cycles from cycle 3 onwards, and at 30 days after the last dose.
- [12] 12-Lead ECG: Attention should be paid to QT, QTcF, and P-R intervals. Performed within 7 days before the first dose (*), on day 1 of each cycle from cycle 2 onwards, and at 30 days after the last dose. Investigators may decide whether to perform additional ECGs, echocardiography, or myocardial zymographic tests if the subject complains of symptoms such as chest pain or palpitations. QTcF can be calculated as: QTcF = QT/(60/heart rate)^{0.33}.
- [13] Echocardiography: within 7 days before the first dose (*).
- [14] Pregnancy test: Serum pregnancy test will be performed for women of childbearing potential. Performed within 7 days before the first dose (*) and on day 1 of every 2 cycles from cycle 3 onwards.
- [15] Tumor imaging evaluation: CT or MRI of lesions in the chest, abdomen, pelvis, and other sites. Brain MRI or CT should be performed for suspected or confirmed brain metastases. MRI or CT confirmation should be performed for bone metastases radiographically or clinically indicated. CT or MRI follow-ups of lesions in the head, chest, abdomen, pelvis, and other sites will be performed at each response evaluation. The CT/MRI examination methods and techniques for a subject shall remain the same throughout the study period.

- ✓ Screening period: tumor evaluations within up to 4 weeks before the first dose and before signing the informed consent may be used as long as they meet the requirements.
- ✓ Study treatment period: Treatment period starting from C1D1 of crossover treatment: The imaging examination cycles will start from C1D1. In the first 16 treatment cycles, imaging examinations will be performed once every 2 cycles (the first assessment will be on C3D1), and once every 4 cycles thereafter. If radiographic progression is noted and pseudoprogression has been ruled out, imaging examinations will no longer be performed; subjects who discontinue the study treatment for reasons other than radiographic progression will still be followed up according to the established cycle. If the previous imaging examination does not show progression and no imaging examination is performed within 4 weeks before the 30-day visit after the last dose, an imaging examination must be performed at the 30-day visit after the last dose. The time window for tumor evaluation is \pm 7 days. Additional tumor evaluations may be performed if PD is suspected (for example, worsening of symptoms).

[16] Dispensation/retrieval of drugs and study treatment: SHR-1210 200 mg, intravenous drip infusion, once every 3 weeks starting from C1D1; if SHR-1210 administration of the current cycle cannot be performed due to adverse events, it can be delayed for up to 7 days from the scheduled administration point. SHR-1210 will not be administered in this cycle if the scheduled administration is delayed for more than 7 days. Apatinib 500 mg, continuous oral administration, once daily. Each treatment cycle lasts for 21 days. The first dose of apatinib is dispensed on C1D1 or one day in advance; subsequent apatinib tablets are allowed to be dispensed at the scheduled time point \pm 3 days; remaining apatinib must be retrieved before each dispensation. For dose interruption due to AEs or other reasons, unscheduled drug dispensation and retrieval are permitted.

[17] Adverse events: Recorded from the date of signing the informed consent form to the end of the safety follow-up period or the start of a new anti-tumor treatment. See [Table 11. Principles of AE/SAE collection and follow-up](#) for details.

[18] Concomitant medication/treatment: Recorded from 28 days before the first dose of study treatment to the end of the safety follow-up period; If a new anti-tumor treatment is started, only concomitant medications for treatment-related adverse events will be recorded thereafter. After the safety follow-up period, only concomitant medications/treatments for adverse events are required to be recorded.

[19] Pharmacokinetics/immunogenicity test: Blood sampling time points for pharmacokinetics and immunogenicity study of SHR-1210: within 0.5 h pre-administration on C1D1, C2D1, C4D1, C6D1, C9D1, and every 4 cycles thereafter, with 4-6 mL of peripheral venous blood collected at each time point; 4-6 mL of peripheral venous blood will be collected once 30 days after the last dose. Blood sampling time points for pharmacokinetics study of apatinib: within 0.5 h pre-administration and 4 h (\pm 10 min) post-administration on C1D1, C2D1, C4D1, and C6D1, with 2-4 mL of peripheral venous blood collected at each time point. The time interval between the administration of apatinib on the day of blood sampling and the previous administration should be no less than 20 h.

[20] Quality of life scoring: Performed within 7 days before the first dose (*), on day 1 of every 2 cycles from cycle 3 onwards, on day 1 of every 4 cycles from cycle 17 onwards, and at 30 days after the last dose.

[21] Diary card dispensing, retrieval, and filling: The subjects will measure blood pressure by themselves or others during the treatment period, and shall fill out the diary card every day to record blood pressure and other discomforts.

[22] Safety follow-up: performed on days 30, 60, and 90 after the last dose. The first safety follow-up visit (day 30) will be carried out at the study center, where the evaluations specified in the protocol will be completed. The second (day 60) and the third (day 90) follow-ups will be performed via phone calls. Information on new anti-tumor treatment, survival, concomitant medications/treatments, and adverse events will be collected.

[23] Survival follow-up: At the end of the safety follow-up period, the subjects will enter the survival follow-up period until death, lost to follow-up, withdrawal of informed consent or termination of the clinical study by the sponsor. During this period, follow-up will be conducted via phone calls or other effective methods once every 2 months to collect information on subject survival and subsequent treatments (if the subjects start a new anti-tumor treatment, the therapeutic regimen and the start and end time should be recorded).

(*) **For the control group, if the examinations of the visit at 21 days after the last dose of chemotherapy are qualified, the results may be used for the visit within 7 days before the first dose of crossover treatment.**

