- [5] Physical examination: Performed within 7 days before the first dose, on day 1 of each cycle from cycle 2 onwards, and at 30 days after the last dose; comprehensive examinations (height, weight, general condition, head and face, neck, chest, abdomen, perineum, extremities, etc.) will be performed; height will be measured only once within 7 days before the first dose and weight will be measured at each visit point (except for C1D1); a targeted physical examination will be performed when clinically indicated.
- [6] Virology: HBsAg (quantitative HBV DNA test if positive); HCV-Ab (quantitative HCV-RNA test if positive) and HIV-Ab: within 28 days before the first dose.
- [7] Hematology: red blood cell count (RBC), hemoglobin (Hb), blood platelet count (PLT), white blood cell count (WBC), absolute neutrophil count (ANC), and lymphocyte count (LYM); tested within 7 days before the first dose, on day 1 of each cycle from cycle 2 onwards, and at 30 days after the last dose.
- [8] Urinalysis: WBC, RBC, and urine protein; tested within 7 days before the first dose, on day 1 of every 2 cycles from cycle 3 onwards, and at 30 days after the last dose. If urine protein is $\geq 2+$, then a quantitative 24-h urine protein test should be added.
- [9] Fecal occult blood: performed within 7 days before the first dose, on day 1 of each cycle from cycle 2 onwards, and at 30 days after the last dose.
- [10] Blood biochemistry: Alanine transaminase (ALT), aspartate aminotransferase (AST), gamma-glutamyl transferase (γ -GT), total bilirubin (TBIL), direct bilirubin (DBIL), alkaline phosphatase (AKP), blood urea nitrogen (BUN) or urea, total protein (TP), albumin (ALB), creatinine (Cr), blood glucose (GLU), serum potassium (K^+), serum sodium (Na^+), serum calcium (Ca^{2+}), serum magnesium (Mg^{2+}), and blood chloride (Cl^-); tested within 7 days before the first dose, on day 1 of each cycle from cycle 2 onwards, and at 30 days after the last dose.
- [11] Coagulation function: Activated partial thromboplastin time (APTT), prothrombin time (PT), thrombin time (TT), fibrinogen (FIB), and international normalized ratio (INR); tested within 7 days before the first dose, on day 1 of every 2 cycles from cycle 3 onwards, and at 30 days after the last dose.

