- [12] Thyroid function: serum thyroid stimulating hormone (TSH), free triiodothyronine (FT3), and free thyroxine (FT4); if FT3 and FT4 are not available, T3 and T4 are allowed for substitution; tested within 7 days before the first dose, on day 1 of each cycle from cycle 2, and at 30 days after the last dose.
- [13] Myocardial zymogram: lactate dehydrogenase (LDH), creatine kinase (CK), and hybrid creatine kinase (CK-MB); tested within 7 days before the first dose.
- [14] 12-Lead ECG: Attention should be paid to QT, QTcF, and P-R intervals. Performed within 7 days before the first dose, on day 1 of each cycle from cycle 2 onwards, and at 30 days after the last dose. QTcF can be calculated as: $QTcF = QT/(60/\text{heart rate})^{0.33}$.
- [15] Echocardiography: within 28 days before the first dose.
- [16] Pregnancy test: Serum pregnancy test will be performed for women of childbearing potential. Performed within 7 days before the first dose and on day 1 of every 2 cycles from cycle 3 onwards.

[17] Tumor imaging evaluation: CT or MRI of lesions in the head, chest, abdomen, pelvis, and other sites. Sites with bone metastasis as shown by bone scans, PET-CT, or clinical indications must also be reexamined by CT or MRI at baseline but no longer undergo bone scan or PET-CT for efficacy follow-up. CT or MRI follow-ups of lesions in the head, chest, abdomen, pelvis, and other sites will be performed at each response evaluation. The CT/MRI examination methods and techniques for a subject shall remain the same throughout the study period.

- ✓ At screening, tumor evaluations (at this study center only) up to 4 weeks before the first dose and before signing the informed consent may be used as long as they meet the requirements.

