[21] Pharmacokinetics/immunogenicity test: Blood sampling time points for pharmacokinetics and immunogenicity study of SHR-1210: within 0.5 h pre-administration on C1D1, C2D1, C4D1, C6D1, C9D1, and every 4 cycles thereafter, with 4-6 mL of peripheral venous blood collected at each time point; 4-6 mL of peripheral venous blood will be collected once at 30 days after the last dose. Blood sampling time points for pharmacokinetics study of apatinib: within 0.5 h pre-administration and 4 h (\pm 10 min) post-administration on C1D1, C2D1, C4D1, and C6D1, with 2-4 mL of peripheral venous blood collected at each time point. The time interval between the administration of apatinib on the day of blood sampling and the previous administration should be no less than 20 h.

[22] Quality of life scoring: Performed within 7 days before the first dose, on day 1 of every 2 cycles from cycle 3 onwards, on day 1 of every 4 cycles from cycle 17 onwards, and at 30 days after the last dose.

- [23] Diary card dispensing, retrieval, and filling: The subjects will measure blood pressure by themselves or others during the treatment period, and shall fill out the diary card every day to record blood pressure and other discomforts.
- [24] Safety follow-up: performed on days 30, 60, and 90 after the last dose. The first safety follow-up visit (day 30) will be carried out at the study center, where the evaluations specified in the protocol will be completed. The second (day 60) and the third (day 90) follow-ups will be performed via phone calls. Information on new anti-tumor treatment, survival, concomitant medications/treatments, and adverse events will be collected.
- [25] Survival follow-up: At the end of the safety follow-up period, the subjects will enter the survival follow-up period until death, lost to follow-up, withdrawal of informed consent or termination of the clinical study by the sponsor. During this period, follow-up will be conducted via phone calls or other effective methods once every 2 months to collect information on subject survival and subsequent treatments (if the subjects start a new anti-tumor treatment, the therapeutic regimen and the start and end time should be recorded).

2 FLOW DIAGRAM OF EXPERIMENT — CONTROL GROUP (DOXORUBICIN + IFOSFAMIDE OR IFOSFAMIDE MONOTHERAPY)

STUDY PROCEDURES	Screening Period		Cycle 1	Cycles 2-6	Cycles 7-16	Cycle 17 and beyond	Safety Visit ^[22]	Survival Follow- Up ^[23]

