- [2] Demographics, medical history, and treatment history: including date of birth, gender, ethnicity, tumor history (tumor diagnosis, surgery, radiotherapy, chemotherapy history, etc.), other concurrent diseases and corresponding treatments. Among them, the tumor history should include: the time of initial diagnosis, pathological diagnosis, clinical staging, etc.
- [3] ECOG PS scoring: Performed within 7 days before the first dose, on day 1 of each cycle in cycles 2-6, and at 21 days after the last dose.
- [4] Vital signs: pulse, respiratory rate, temperature, and blood pressure. Performed within 7 days before the first dose, on day 1 of each cycle in cycles 2-6, and at 21 days after the last dose.
- [5] Physical examination: Performed within 7 days before the first dose, on day 1 of each cycle in cycles 2-6, and at 21 days after the last dose; comprehensive examinations (height, weight, general condition, head and face, neck, chest, abdomen, perineum, extremities, etc.) will be performed; height will be measured only once within 7 days before the first dose and weight will be measured at each visit point; a targeted physical examination will be performed when clinically indicated.

- [6] Virology: HBsAg (quantitative HBV DNA test if positive); HCV-Ab (quantitative HCV-RNA test if positive) and HIV-Ab.
- [7] Hematology: red blood cell count (RBC), hemoglobin (Hb), blood platelet count (PLT), white blood cell count (WBC), absolute neutrophil count (ANC), and lymphocyte count (LYM); tested within 7 days before the first dose, on day 1 of each cycle in cycles 2-6, and at 21 days after the last dose.
- [8] Urinalysis: WBC, RBC, and urine protein. If urine protein is $\geq 2+$, then a quantitative 24 h urine protein test should be added; performed within 7 days before the first dose, on day 1 of each cycle in cycles 2-6, and at 21 days after the last dose.
- [9] Fecal occult blood: performed within 7 days before the first dose, on day 1 of each cycle in cycles 2-6, and at 21 days after the last dose.

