- [10] Blood biochemistry: Alanine transaminase (ALT), aspartate aminotransferase (AST), gamma-glutamyl transferase (γ -GT), total bilirubin (TBIL), direct bilirubin (DBIL), alkaline phosphatase (AKP), blood urea nitrogen (BUN) or urea, total protein (TP), albumin (ALB), creatinine (Cr), blood glucose (GLU), serum potassium (K^+), serum sodium (Na^+), serum calcium (Ca^{2+}), serum magnesium (Mg^{2+}), and blood chloride (Cl^-); tested within 7 days before the first dose, on day 1 of each cycle in cycles 2-6, and at 21 days after the last dose.
- [11] Coagulation function: Activated partial thromboplastin time (APTT), prothrombin time (PT), thrombin time (TT), fibrinogen (FIB), and international normalized ratio (INR); tested within 7 days before the first dose, on day 1 of each cycle in cycles 2-6, and at 21 days after the last dose.
- [12] Thyroid function: serum thyroid stimulating hormone (TSH), free triiodothyronine (FT3), and free thyroxine (FT4); if FT3 and FT4 are not available, T3 and T4 are allowed for substitution; tested within 7 days before the first dose, and at 21 days after the last dose.
- [13] Myocardial zymogram: lactate dehydrogenase (LDH), creatine kinase (CK), and hybrid creatine kinase (CK-MB); tested within 7 days before the first dose, on day 1 of each cycle in cycles 2-6, and at 21 days after the last dose.
- [14] 12-Lead ECG: Attention should be paid to QT, QTcF, and P-R intervals. Performed within 7 days before the first dose, on day 1 of each cycle in cycles 2-6, and at 21 days after the last dose. Investigators may decide whether to perform additional ECGs and/or myocardial zymographic tests if the subject complains of symptoms such as chest pain or palpitations. QTcF can be calculated as: $QTcF = QT/(60/\text{heart rate})^{0.33}$.
- [15] Echocardiography: performed within 28 days before the first dose, on day 1 of each cycle in cycles 2-6, and at 21 days after the last dose. Additional echocardiography may be performed if the subject complains of symptoms such as chest pain or palpitations.
- [16] Pregnancy test: Serum pregnancy test will be performed for women of childbearing potential. Performed within 7 days before the first dose, on day 1 of every 2 cycles in cycles 3-6, and at 21 days after the last dose.

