5.5.2 Adverse event

AEs will be classified by treatment stage (before and after study treatment).

All AEs will be coded with MedDRA (version, 23.1). and graded using NCI-CTCAE v4.03. For the same SOC and/or PT, multiple cases of the same events that occur in one subject will be counted only once. For the same AE reported in one subject multiple times but varying in CTCAE grade, the AE of the greatest grade will be enumerated.

AEs will be sorted by incidence from high to low based on SOC, and PT under each SOC. If the incidence of ≥ 2 PT is equal, the AEs will be sorted alphabetically. If there is no AE under a SOC or PT, then analysis will not be conducted.

A treatment-emergent adverse event (TEAE) is defined as any adverse event that occurs after the start of study treatment. Only TEAEs will be summarized. All AEs will be listed. AEs with completely missing onset time will be treated as TEAEs.

For AEs occurring after the start of study treatment, treatment-related AEs include those whose causality with the study drug is definitely related, possibly related, or indeterminable; if the causality assessment is missing, then the AE will be deemed treatment-related for analysis.

In a listing of AEs, TEAEs will be analyzed by group, and frequencies and proportions will be statistically described. AEs will be summarized using descriptive statistics according to Hengrui's Statistical Analysis Reporting Standards, including but not limited to the following contents:

- Any TEAE
- Treatment-related AEs (TRAEs)
- Any TESAE
- Treatment-related SAEs (TRSAEs)
- Any SAE
- Any drug-related SAE
- TEAEs resulting in dose reduction, dose interruption followed by reduction, interruption, or treatment discontinuation
- TRAEs resulting in dose reduction, dose interruption followed by reduction, interruption, or treatment discontinuation
- TEAEs resulting in death
- Immune-related adverse events ("reactive capillary endothelial proliferation" will all be considered immune-related events)?
- Was hormone therapy used?

The incidence of AE is calculated based on the number of subjects having an AE, instead of the number of AE episodes.

All AEs will be listed. Drug-related AEs, AEs resulting in treatment discontinuation, AEs resulting in dose reduction or dose interruption followed by reduction or treatment interruption, and death will be listed.

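### Several safety checks run on different schedules in the two arms, so crude by-arm incidence of test-detected and diary-prompted adverse events partly reflects how often subjects were checked

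*Protocol*

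**What the plan says.** **Diary and home blood pressure.** In the investigational arm (Protocol section 1, footnote [23]) "The subjects will measure blood pressure by themselves or others during the treatment period", and each subject "shall fill out the diary card every day to record blood pressure and other discomforts". Section 3, footnote [21], repeats this for crossover treatment. The control chart and its footnotes (section 2) contain no diary item.

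**Urinalysis and coagulation.** For investigational urinalysis (section 1, footnote [8]) the schedule is "tested within 7 days before the first dose, on day 1 of every 2 cycles from cycle 3 onwards, and at 30 days" (counted from the final dose); coagulation (footnote [11]) is the same. In control (section 2, footnotes [8] and [11]) both are done "on day 1 of each cycle in cycles 2-6, and at 21 days after the last dose".

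**Thyroid.** Section 1, footnote [12], has "on day 1 of each cycle from cycle 2, and at 30 days after the last dose" for the investigational arm, whereas that section's chart and section 11.2.1 have every second cycle from cycle 3. Control is tested at baseline and 21 days after the last dose only (section 2, footnote [12]).

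**Echocardiography and cardiac enzymes.** Investigational: "Echocardiography: within 28 days before the first dose" (section 1, footnote [15]). Control: "Echocardiography: performed within 28 days before the first dose, on day 1 of each cycle in cycles 2-6", and again at day 21 (section 2, footnote [15]). Control enzymes follow the same on-treatment pattern. The investigational chart has enzymes at baseline only, but section 11.3.1 adds them at the day-30 visit.

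**Analysis.** Comparing safety between arms is a secondary objective (Protocol 6.1.2, SAP 2.2.2). SAP 5.5.2 states that "TEAEs will be analyzed by group, and frequencies and proportions will be statistically described", counts subjects with any event, and defines a treatment-emergent event as anything after the start of study treatment. Laboratory results, vital signs and echocardiography are only listed (SAP 5.5.3, 5.5.4, 5.5.8).

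**The concern.** An abnormality that causes no symptoms enters the event table only if someone looks for it. Where one arm is looked at more often, its incidence rises even if the true rates are equal.

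The imbalance has no single direction. Raised blood pressure, thyroid disturbance and minor symptoms are sought more in the investigational arm. Urine, coagulation, on-treatment enzyme and ejection-fraction findings are sought more in control. When a control subject crosses over, the diary and periodic thyroid tests start, urine and coagulation tests become less frequent, and per-cycle echocardiography and enzymes stop. The definition of a treatment-emergent event has no cut at that point, so events found under the second schedule can be counted under the control group.

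Protocol 14.4.5 promises descriptive summaries of abnormal laboratory values and of vital-sign values and changes. The SAP replaces these with listings. For blood pressure, urine, coagulation, thyroid and enzyme findings, the event table is then the only tabulated comparison between arms, and it is the one most exposed to unequal checking.

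**Working it through.** The plan states no figure on this point, so there is none to reproduce. I counted scheduled checks and then illustrated their effect.

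**Step 1. Scheduled post-baseline checks**, for a subject who completes six 21-day cycles and attends the first safety visit (day 30 investigational, day 21 control).

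| Check | Investigational | Control |
|---|---|---|
| Urinalysis | C3, C5, day 30 = 3 | C2–C6, day 21 = 6 |
| Coagulation | C3, C5, day 30 = 3 | C2–C6, day 21 = 6 |
| Thyroid | 3 (chart, 11.2.1) or C2–C6 + day 30 = 6 (footnote [12]) | day 21 = 1 |
| Cardiac enzymes | 0 (chart) or day 30 = 1 (11.3.1) | C2–C6, day 21 = 6 |
| Echocardiography | 0 | C2–C6, day 21 = 6 |
| Home blood pressure | 6 × 21 = 126 | 0 |
| Clinic blood pressure | 6 | 6 |

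Beyond cycle 6, control visits keep the same content (section 2, footnote [18]), so the gap persists.

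**Step 2. Chance that a scheduled test falls inside an episode.** Assumptions, none from the documents: onset uniform over weeks 0–18, episode length D weeks, no unscheduled tests, no visit windows. Control tests fall at weeks 3, 6, 9, 12, 15 and 18.43 (day 21 after the fourth ifosfamide day of cycle 6). Investigational two-cycle tests fall at weeks 6, 12 and 22.29 (day 30 after apatinib ends at week 18). The share detected is the length of onset time within D weeks before some test, divided by 18.

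Urinalysis and coagulation:
- D = 3. Investigational: onsets in 3–6 and 9–12, so 6/18 = 33%. Control: onsets in 0–15 and 15.43–18, so 17.57/18 = 98%.
- D = 6. Investigational: 0–12 and 16.29–18, so 13.71/18 = 76%. Control: 100%.
- D = 26. 100% in both arms.

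Thyroid:
- D = 3. Investigational: 33% by the chart, or 15/18 = 83% by footnote [12]. Control: 2.57/18 = 14%.
- D = 6. Investigational: 76%, or 16.71/18 = 93%. Control: 5.57/18 = 31%.
- D = 26. 100% in both arms.

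Echocardiography: 0% against 98% at D = 3, and 0% against 100% at D = 26, because no post-baseline echocardiogram is scheduled in the investigational arm.

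**Step 3. A second illustration.** If each check independently has probability q of a positive result, equal in both arms, then P(at least one) = 1 − (1 − q)^k for k checks.

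| q (assumed) | k = 1 | k = 3 | k = 6 |
|---|---|---|---|
| 2% | 2.0% | 5.9% | 11.4% |
| 5% | 5.0% | 14.3% | 26.5% |
| 10% | 10.0% | 27.1% | 46.9% |

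With 3 against 6 checks and equal true rates, the tabulated incidence differs by a factor of 1.7 to 1.9 (46.9/27.1 = 1.73; 11.4/5.9 = 1.93).

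**Step 4. What is not affected.** Haematology, biochemistry, fecal occult blood, clinic vital signs, physical examination and 12-lead ECG are done every cycle from cycle 2 in the investigational arm and every cycle in cycles 2–6 in control, with the same content in later control treatment cycles.

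**The case against.** Monitoring is fitted to drugs with different toxicities, and the safety analysis is descriptive: no test, no alpha, and no bearing on the primary endpoint. That stands. But descriptive incidence by arm is how the comparison objective will be answered, and nothing here asks for monitoring to change.

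Three stronger readings are tempting and should be resisted.

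- A reader might infer that every abnormal result becomes an adverse event. Protocol 13.1.1 and SAP 4.2.1 count only clinically significant laboratory findings, so the percentages above describe detection of abnormalities, not of events.
- A reader might infer that ejection-fraction falls and enzyme rises can appear only in control. Section 11.3.1 schedules enzymes at the investigational day-30 visit, section 11.1 allows echocardiography when clinically indicated, and the chart notes let investigators add examinations. The restriction to control holds only for scheduled on-treatment checks.
- A reader might infer that crossover safety is ignored. Protocol 14.4.9 plans a separate descriptive summary and SAP 2.2.3 keeps the objective. However, SAP section 5 contains no matching analysis, and a separate summary would not remove the imbalance before crossover.

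It is also fair that persistent findings are mostly caught later, since SAP 5.5.2 counts a subject once however late the event is found.

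**Conclusion.** The point holds in a limited form. For blood pressure, diary-prompted symptoms, thyroid, urine, coagulation, cardiac enzymes and ejection fraction, between-arm differences in crude incidence partly reflect checking frequency. The documents do not support saying that these rates merely measure how often subjects were checked, nor that the safety comparison as a whole is distorted.

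The schedule counts come directly from the documents: 3 against 6 for urinalysis and coagulation; 3 or 6 against 1 for thyroid; 0 or 1 against 6 for enzymes; 0 against 6 for echocardiography. The detection percentages rest on assumed episode lengths. For urine and coagulation the gap is large at 3 weeks, moderate at 6 weeks and absent at 26 weeks. The effect is therefore greatest for transient or silent findings and small for lasting ones that an end visit catches. Echocardiography is the exception, because the investigational arm has no scheduled end-visit examination. The SAP should deal with this before database lock; it does not threaten the primary analysis.

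**What to change.** In the SAP:

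1. Keep the all-source table of treatment-emergent events in 5.5.2, but show control-arm events before and after crossover separately.
2. Add by-arm tables of abnormal values at visits common to both arms: day-1 clinic blood pressure; urinalysis and coagulation at C3D1, C5D1 and the first safety visit; thyroid and cardiac enzymes at the first safety visit. Note that this visit is day 30 in one arm and day 21 in the other.
3. Footnote the event table to say that on-treatment echocardiography and enzymes were scheduled only in control, that the diary and home blood pressure were used only with SHR-1210 + apatinib, and that the corresponding incidences are not directly comparable.
4. Do not plan a table of diary-only events unless the eCRF records how an event was detected. The event details listed in Protocol 13.1.1 include no such item.

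In the Protocol, reconcile the thyroid frequency (section 1, footnote [12], against its chart and 11.2.1) and the day-30 enzymes (section 1 chart against 11.3.1). The second table in item 2 relies on the outcome for enzymes.

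The cost is SAP wording and a few tables from scheduled measurements, with fewer events in the matched tables than in the full one. No visit or test changes.
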